2. Patients will be transferred to the CTICU intubated and on a propofol infusion and/or dexmedetomidine (Precedex) from the operating room. Both meds are used SOC.
3. Upon CTICU arrival, the patients surgeon and CTICU intensivist will determine if patient is able to proceed with fast-track extubation. Determination of continued eligibility based on the post-recruitment pre-randomization exclusion criteria will be determined by a member of the study team. Eligible patients will be randomized, investigational pharmacy will be contacted for study drug and within 30 minutes of the ICU admission, propofol will be discontinued. Precedex may be continued per clinical discretion.
4. The participant will be randomized to receive Sugammadex or placebo. The enrolled patients will be assigned to the study and control arms in a 1:1 ratio.
5. IDS will provide the Sugammadex (2mg/kg) vs. Placebo in a syringe. A qualitative train-of-four measurement will be obtained. The administration of the study drug and placebo compounds will be performed by CTICU nurses who will receive the drugs in a blinded fashion from the departmental research pharmacy. The study drug will be supplied by Merck.
6. The clinical care provider has the discretion to determine the appropriate ventilation settings on a case-by-case basis, in accordance with the suggestion that patients will be initiated on SIMV rate of 14 with 60% FiO₂, tidal volumes 8-10 ml/kg and PEEP of 7.
7. Ten minutes after the drug administration, if the patient can lift their head and remains hemodynamically stable, the patient will be switched to CPAP mode of ventilation for 30 minutes. At the end of the CPAP trial tidal volumes, Rapid Shallow Breathing Index (RSBI) and ABG will be assessed. The patient will be extubated if he/she is not hypoxic/ hypercarbic, has RSBI<100 and has TV >300 cc.
8. If a patient fails the 30-minute CPAP criteria, the ICU intensivist will be immediately notified. Every attempt will be made to correct the underlying cause of CPAP failure, and a prompt reassessment will be made as deemed appropriate by the intensivist to reattempt CPAP versus continuing controlled mechanical ventilation.

Study participation will end when the patient is successfully extubated. AE assessment will be performed in the period immediately following extubation.

5. Genetic Testing N/A

6. **Subject Population:** Provide a detailed description of the types of human subjects who will be recruited into this study.

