4. Determination that the patient will require prolonged mechanical ventilation possibly requiring muscle relaxation based on the intraoperative course and clinical judgment of the study PI or collaborating intensivists.
5. Intraoperative hypoxia or on arrival to the ICU. (Please see Study Flowchart).
6. Cardiac arrest
7. Sudden arrhythmia (Ventricular tachycardia runs/sudden bradycardia with improper pacemaker detection/function) precluding fast-track extubation protocol.
8. Need for two or more inotrope initiation precluding fast-track protocol. Only a single vasopressor/inotrope may be initiated without excluding the subject.
9. Postoperative ST changes.

10. A positive standard of care pregnancy test during your pre-operative evaluation

9. How will **eligibility** be determined, and by whom?

Eligibility at pre-op and post-op will be based on protocol specific inclusion and exclusion criteria and will be determined by the PI or Sub-I's in collaboration with the ICU attending physician

10. **Risks:** Describe the reasonably foreseeable risks, including risks to subject privacy, discomforts, or inconveniences associated with subjects participating in the research.

Sugammadex is generally safe and well tolerated. Potential risks associated with sugammadex are: hypersensitivity, including anaphylaxis/anaphylactic shock – previous trials suggest this risk is small. Cardiac arrhythmias including bradycardia & tachycardia where intervention is rare and responsive to usual treatment. Other reported risks include nausea, vomiting, constipation.

Bleeding was originally thought to be a side effect, but studies have since showed that Sugammadex falsely elevates the PTT without increasing bleeding risk. (see reference on last page.)

11. **Minimizing Risks:** Describe the way the above-mentioned risks will be minimized.

Patients will all be in a critical care environment and monitored very closely including: blood pressure, heart rate, and chest tube output will be tracked from arrival to the CTICU until extubation per ICU protocol. Subtle changes in the patient's hemodynamic status are easily seen and treated if necessary.

12. **Data and Safety Monitoring Plan:** Include an appropriate Data and Safety Monitoring Plan (DSMP) based on the investigator's risk assessment stated below. (Note: the HIC will make the final determination of the risk to subjects.)

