- e.) Unrelated: Adverse event is clearly not related to investigational procedures(s)/agent(s).

4. Plan for Grading Adverse Events:

The following scale will be used in grading the severity of adverse events noted during the study:

1. Mild adverse event
2. Moderate adverse event
3. Severe

5. Plan for Determining Seriousness of Adverse Events:

Serious Adverse Events:

In addition to grading the adverse event, the PI will determine whether the adverse event meets the criteria for a Serious Adverse Event (SAE). An adverse event is considered serious if it results in any of the following outcomes:

1. Death;
2. A life-threatening experience in-patient hospitalization or prolongation of existing hospitalization;
3. A persistent or significant disability or incapacity;
4. A congenital anomaly or birth defect; OR

5. Any other adverse event that, based upon appropriate medical judgment, may jeopardize the subject's health and may require medical or surgical intervention to prevent one of the other outcomes listed in this definition.

An adverse event may be graded as severe but still not meet the criteria for a Serious Adverse Event. Similarly, an adverse event may be graded as moderate but still meet the criteria for an SAE. It is important for the PI to consider the grade of the event as well as its "seriousness" when determining whether reporting to the IRB is necessary.

Only the following adverse events will be tracked. These AE's will trigger an immediate DSMB review; any incidence of anaphylaxis; unexplained hypotension requiring initiation of pressors; cardiac pacing within 5 minutes of drug administration; tachycardia, bradycardia or onset of atrial fibrillation; or increases in chest tube output considered clinically significant by the critical care team. The DSMB will be notified within 2 business days of determination by telephone or email. A written report will be provided within 7 days of the determination. Any incidents meeting SAE criteria will be reported per the IRB reporting policy.

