These UPIRSOs/SAEs will be reported to the IRB in accordance with IRB Policy 710, using the appropriate forms found on the website. All related events involving risk but not meeting the *prompt* reporting requirements described in IRB Policy 710 should be reported to the IRB in summary form at the time of continuing review. If appropriate, such summary may be a simple brief statement that events have occurred at the expected frequency and level of severity as previously documented. In lieu of a summary of external events, a current DSMB report can be submitted for research studies that are subject to oversight by a DSMB (or other monitoring entity that is monitoring the study on behalf of an industry sponsor).

7. Plan for reporting adverse events to co-investigators on the study, as appropriate the protocol's research monitor(s), e.g., industrial sponsor, Yale Cancer Center Data and Safety Monitoring Committee (DSMC), Protocol Review Committee (PRC), DSMBs, study sponsors, funding and regulatory agencies, and regulatory and decision-making bodies.

For the current study, the following individuals, funding, and/or regulatory agencies will be notified (choose those that apply):

- All Co-Investigators listed on the protocol.
- Study Grantor (Merck)
- Other Data Safety Monitoring Board (DSMB)
- Yale University IRB

The principal investigator [name] will conduct a review of all adverse events upon completion of every study subject. The principal investigator will evaluate the frequency and severity of the adverse events and determine if modifications to the protocol or consent form are required.

See also DSMB charter attached.

13. Statistical Considerations: Describe the statistical analyses that support the study design.

Variables/Time Points of Interest

The primary outcome is the time to extubation, which will be the duration from arrival to the ICU to the extubation time.

Proposed statistical test/analysis: Positively skewed variables will be log-transformed prior to hypothesis testing. For the primary outcome, a two-sided Student's t-test will be used to compare

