**Adverse Experience Reporting:** Throughout the duration of the study, researchers will adhere to good clinical practice and the guidelines of the institution. Patient vitals will be continuously monitored during and after the administration of the test drug. A data and safety monitoring board (DSMB) consisting of the head nurse and a senior critical care staff will meet monthly to discuss any serious events. Any incidence of anaphylaxis or unexplained hypotension requiring initiation of pressors or cardiac pacing within 5 minutes of drug administration will be reported and evaluated. Increases in chest tube output considered clinically significant by the critical care team will be noted. Any of these adverse events will trigger an analysis by the DSMB. If the DSMB determines that study drug may be causing an increase in adverse events, the study will be suspended until the DSMB is able to fully review the events and make a recommendation in consultation with the Yale Human Investigations Committee. The local Merck research

representative will also be notified about the events. If the data monitoring board and/or institutional review board (IRB) view that the study is unsafe, the study will be discontinued.

**Specific Safety Events to Be Reported During Manuscript Preparation:** For manuscript preparation, the rates of hypotension, anaphylaxis, and bleeding (i.e. Chest Tube output) will be reported and compared between active and placebo groups.

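### The plan does not say whether the primary outcome ends at first or final extubation, and it does not collect or compare reintubation by arm

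*Protocol*

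**What the plan says.** - **Endpoint.** Protocol Section I, item 13, and the SAP under Variables/Time Points of Interest use the same sentence: "The primary outcome is the time to extubation, which will be the duration from arrival to the ICU to the extubation time". Neither gives a first-versus-final rule, a reintubation-free window, or a way to handle a reintubated patient.
- **End of participation.** Protocol Section I, item 4: "Study participation will end when the patient is successfully extubated". The next sentence adds that "AE assessment will be performed in the period immediately following extubation". Success is not defined, and the length of that period is not given.
- **Monitoring.** Under item 11, blood pressure, heart rate and "chest tube output will be tracked from arrival to the CTICU until extubation per ICU protocol".
- **Adverse events.** Item 12, in the part on seriousness: "Only the following adverse events will be tracked". The list covers anaphylaxis, unexplained hypotension needing pressors, pacing soon after dosing, rate or rhythm disturbance, and increased chest tube output. Reintubation and respiratory failure are not on it. The same part adds: "Any incidents meeting SAE criteria will be reported per the IRB reporting policy".
- **Between-arm safety comparison.** The SAP, under the safety events for the manuscript, says that "the rates of hypotension, anaphylaxis, and bleeding (i.e. Chest Tube output) will be reported and compared between active and placebo groups".

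The only failure described is failing the CPAP trial, which comes before extubation. Reintubation is not mentioned in the supplied text of either document.

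**The concern.** The trial tests whether a drug brings extubation forward. The benefits named in Section V (less time in critical care, possibly less pneumonia) depend on the patient staying extubated. An earlier extubation that has to be undone does not deliver them. With the clock's end point ambiguous and reintubation outside both the tracked and the compared events, a positive result could not be accompanied by evidence that the extubations were durable. The protocol's title promises efficacy and safety, and this is a safety question that the main result itself raises.

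**Working it through.** **1. The plan's own figure.** Inputs from item 13: difference 2 h, SD 2.89 h, two-sided alpha 0.05, power 90%. The normal approximation gives n = 2 × (1.96 + 1.2816)² × 2.89² / 2² = 43.9, so 44 per arm. The exact t calculation gives 44.86, so 45. Power at 45 per arm is 90.1% (exact t) or 90.7% (normal). The stated 45 per group reproduces, and this point does not affect it.

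**2. One hypothetical patient.** Suppose extubation at 4 h, then reintubation, then final extubation at 28 h. Read literally, item 13 permits 4 h. If the success condition in item 4 is read into the endpoint, the value becomes 28 h. One patient has two possible primary values, and no rule chooses between them.

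**3. Whether another provision closes the gap.**
- The assessment after extubation has no stated length, and the tracked list is closed.
- A reintubation that met the serious-event criteria would go to the IRB, and the SAP has the DSMB discuss serious events monthly. Neither is a by-arm outcome.
- Reporting as an unanticipated problem needs three criteria at once (unexpected, at least possibly related, and suggesting greater risk than known). A reintubation need not meet all three.
- Intention to treat settles who is analysed, not how long they are observed.
- The Cox sensitivity analysis uses the same outcome. The per-protocol analysis concerns exclusions before dosing.

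**4. Illustrative size.** The documents give no reintubation rate or added hours, so both are assumed. Let k be the net extra reintubations in one arm of 45, and X the hours between first and final extubation. The shift in that arm's mean time to final extubation is kX/45.

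| k | X = 12 h | X = 24 h | X = 48 h |
|---|---|---|---|
| 1 | 0.27 h | 0.53 h | 1.07 h |
| 2 | 0.53 h | 1.07 h | 2.13 h |
| 4 | 1.07 h | 2.13 h | 4.27 h |

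One patient at 24 h is 0.53/2, about 27% of the target difference.

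**5. The log scale.** Both documents log-transform positively skewed variables. Take a patient at an active-arm mean of 8.39 − 2 = 6.39 h with 24 h added. The shift is ln(30.39/6.39)/45 = 1.559/45 = 0.035. The target is roughly ln(8.39/6.39) = 0.272. The shift is about 13% of the target, roughly half the raw-scale share.

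**6. Power if final extubation were analysed.** These come from 20,000 simulated trials, 45 per arm, means 6.39 and 8.39 h, SD 2.89 h. Times are normal for the raw-scale test and lognormal for the log-scale test. Reintubation rates are assumed.

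| Active / placebo rate, hours added | Raw-scale t-test | Log-scale t-test |
|---|---|---|
| None (same as first extubation) | 90% | 96% |
| 2% / 2%, 12 h | 80% | 94% |
| 2% / 2%, 24 h | 60% | 90% |
| 5% / 2%, 12 h | 57% | 84% |
| 5% / 2%, 24 h | 26% | 70% |

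With equal rates the true raw mean difference stays at 2 h, so the raw-scale loss there is added variance, not bias.

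**7. Chance that the question arises.** With 90 randomized, the probability of at least one reintubation is 1 − (1 − p)⁹⁰: 60%, 84% or 99% for assumed p of 1%, 2% or 5%.

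**The case against.** A reader might infer that a patient who fails an early extubation is scored as a fast success. The documents state no such rule. Item 13 is silent on first versus final, and the success wording in item 4 can be read to keep a promptly reintubated patient in the study. This is an undefined term, not a declared scoring rule.

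A reader might also infer that such a failure would never be recorded. That goes too far: there is an assessment after extubation, a serious-event route, and an investigator review of adverse events when each subject completes. What is missing is systematic collection and comparison by arm.

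The strongest objection concerns bias. Nothing in the documents predicts more failed extubations on active drug. Both arms pass the same pre-extubation criteria, nurses give the drug blinded, and the SAP keeps the clinical team blind to the neuromuscular measurements. Residual block on placebo is an equally plausible cause of failure. This objection stands, and no direction is claimed here.

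It also stands that first extubation is a legitimate primary outcome, consistent with the stated aim. Building a reintubation-free window into the primary event is a design trade-off, not a correction. Finally, the study flowchart and DSMB charter were not supplied, and part of the SAP was missing from the text examined, so a definition there cannot be excluded. The endpoint and safety sections that were available contain none.

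**Conclusion.** The point holds as a gap in definition and data collection. The endpoint can be read two ways for a reintubated patient, and neither document collects or compares reintubation by arm. Followed as written, the trial could show earlier extubation without showing whether it lasted.

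The size is illustrative only: 0.27 to 1.07 h on the raw scale per net extra reintubation in an arm of 45, for 12 to 48 added hours, and less on the log scale. A reader might infer that reintubation would cancel the 2 h benefit. The arithmetic reaches that only with, for example, four cases against none at 24 h each on the raw scale (2.13 h). The documents support neither that split nor that duration. The sample size is unaffected. This is a worthwhile, inexpensive improvement and not evidence that the planned result would be biased.

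**What to change.** 1. In Protocol item 13 and the SAP, state that the primary outcome is time from ICU arrival to first extubation. Either define success in the end-of-participation sentence of item 4 or remove the word.
2. Add reintubation within a stated window, taken from the ICU chart, to the tracked list in item 12 and to the between-arm comparison in the SAP.
3. Add a sensitivity analysis on time to final extubation, with its scale stated in advance. The simulated power above is a reason to keep this analysis secondary.

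Cost: a few sentences in each document and a small addition to chart abstraction. Data collection would run a day or two past extubation, so the end-of-participation wording, and possibly the consent, needs a small amendment. No dose or clinical rule changes.

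### The closed list of tracked adverse events leaves out non-anaphylactic hypersensitivity, nausea and vomiting, which the protocol names as sugammadex risks, and conflicts with its general monitoring statements

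*Protocol*

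**What the plan says.** **Named risks.** Protocol Section I, item 10 gives three groups of risk for the study drug:
- "Potential risks associated with sugammadex are: hypersensitivity, including anaphylaxis/anaphylactic shock"
- "Cardiac arrhythmias including bradycardia & tachycardia where intervention is rare and responsive to usual treatment"
- "Other reported risks include nausea, vomiting, constipation"

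**Tracked events.** Item 12, sub-item 5 restricts recording: "Only the following adverse events will be tracked". The list that follows also serves as the list of triggers for immediate DSMB review. It consists of "any incidence of anaphylaxis; unexplained hypotension requiring initiation of pressors; cardiac pacing within 5 minutes of drug administration"; "tachycardia, bradycardia or onset of atrial fibrillation"; and "increases in chest tube output considered clinically significant by the critical care team". Anything that meets the criteria for a serious adverse event goes to the IRB, listed or not.

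**General monitoring.** Elsewhere in item 12 the scope is wider. The plan is justified by the possibility of expected and unexpected events of any seriousness. Sub-item 3 has adverse events monitored and attributed for every subject, sub-item 4 provides a mild grade, and sub-item 7 has the principal investigator review all adverse events after each subject and judge their frequency and severity.

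**Analysis.** Protocol item 13 and the SAP's statistical methods plan a chi-square or Fisher's exact test for categorical adverse events, without naming them. The SAP's section on safety events for the manuscript says that "the rates of hypotension, anaphylaxis, and bleeding (i.e. Chest Tube output) will be reported and compared between active and placebo groups".

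**The concern.** A closed list decides what data will exist. If an effect that the protocol attributes to the drug is not on the list and the event is not serious, nothing obliges anyone to write it down, and no later analysis can bring it back. Safety is part of this trial's title, and the Background says that use after cardiac surgery is limited for want of supporting data. A safety account that is silent on some of the plan's own named risks is therefore incomplete by rule.

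There is also a practical conflict. Staff cannot both restrict recording to the list in sub-item 5 and supply the principal investigator with all adverse events for the review in sub-item 7. Which instruction prevails would be settled at the bedside, possibly differently from one patient to the next.

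**Working it through.** **1. Named risks against tracked and reported events.** The first column comes from Protocol item 10, the second from item 12 sub-item 5, and the third from the SAP's manuscript list.

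| Effect named as a risk | On the tracked list | In the SAP manuscript comparison |
|---|---|---|
| Anaphylaxis | yes | yes |
| Hypersensitivity short of anaphylaxis | no | no |
| Bradycardia | yes | no |
| Tachycardia | yes | no |
| Nausea | no | no |
| Vomiting | no | no |
| Constipation | no | no |

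Counted singly, 3 of 7 are tracked. With hypersensitivity and anaphylaxis taken as one item, 3 of 6 are tracked. The list also carries hypotension, which the Background raises, and chest tube output, which relates to the bleeding question discussed under item 10.

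**2. Can another route recover the omitted events?**
- Serious-event reporting covers only events that meet the seriousness criteria. A non-serious skin reaction, or vomiting after extubation, need not do so.
- A hypersensitivity reaction with tachycardia, or with hypotension needing pressors, would meet a listed event. It would be recorded as that event, with no requirement to record it as hypersensitivity.
- The general chi-square or Fisher test can cover the tracked arrhythmias, although the manuscript list omits them. It cannot compare events that were not recorded.
- The general monitoring statements in sub-items 3 and 7 would recover the omitted events if they prevailed, but sub-item 5 says the opposite.

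**3. Is there a window in which to observe them?** The Research Plan (item 4) ends participation at successful extubation and places the adverse-event assessment just after it, without a stated duration. Hypersensitivity can be observed from dosing. Nausea and vomiting can be noted at the assessment, but how many would fall inside it is unknown. Constipation cannot reasonably be assessed in this window.

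**4. What about 45 per arm can show.** The plan's figure reproduces. With a difference of 2 h, SD 2.89 h, two-sided alpha 0.05 and 90% power, the normal approximation gives 2 × (1.960 + 1.282)² × 2.89² / 2² ≈ 43.9, so 44 per group. The t-based calculation gives 44.86, so 45, with 90.1% power at 45.

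For safety counts at n = 45 per arm:
- *No events in 45.* The upper limit for the true rate is 1 − 0.05^(1/45) = 6.4% (one-sided 95%) or 1 − 0.025^(1/45) = 7.9% (upper end of a two-sided 95% interval). For anaphylaxis, which is tracked, such a limit can be stated. For an untracked effect there is no numerator, so no limit can be stated at all.
- *Two events against none (illustration).* Fisher's exact two-sided p = 2 × (45 × 44)/(90 × 89) = 2 × 0.247 = 0.49.
- *Power for assumed rates (illustration).* With the pooled variance under the null and the separate variances under the alternative, power = Φ[(|p1 − p0| − 1.96 × √(2p̄(1 − p̄)/45)) / √((p0(1 − p0) + p1(1 − p1))/45)]. For 20% against 30% this is Φ[(0.100 − 0.179)/0.0907] = 19%. For 20% against 40% it is Φ[(0.200 − 0.189)/0.0943] = 54%.

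The documents give no rate for any of the omitted effects, so the expected number of unrecorded events cannot be calculated.

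**The case against.** The strongest reply is that a short, focused list is a legitimate choice for a marketed drug in a 90-patient trial. The list holds the acute, serious concerns: anaphylaxis, haemodynamic events, arrhythmias and bleeding. Serious events are reported whatever their type, and the protocol elsewhere promises general monitoring. The added counts would have little power, and the assessment window is short.

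Much of this stands. The list is clinically coherent, and the low power is real. Low power, however, argues for descriptive counts and not for recording nothing; it applies equally to anaphylaxis, which is tracked. The general monitoring statements do not answer the point either, because they contradict the closed list.

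A reader might go further and infer that the trial cannot compare most of the effects it warns patients about. The documents do not support this. The arrhythmias are named and tracked, so most is true only on the finest count (4 of 7 untracked), and the consent form is not available to show what patients are told. A reader might also suppose that milder hypersensitivity is the commoner form, which 45 patients would be likely to show. Nothing in the documents says so: item 10 calls the risk small in a sentence that covers hypersensitivity including anaphylaxis.

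**Conclusion.** The point holds in a limited form. As written, sub-item 5 excludes from recording three effects that the protocol names as drug risks and that could be observed at least in part: non-serious hypersensitivity short of anaphylaxis, nausea and vomiting. Constipation is also excluded, but the follow-up could not capture it. Sub-item 5 conflicts with sub-items 3 and 7 of the same monitoring plan, and the sections must be reconciled. A smaller gap is that the SAP's manuscript comparison omits the arrhythmias that the protocol does track.

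The size is 3 of 7 named effects tracked, or 3 of 6 with hypersensitivity and anaphylaxis merged. The primary outcome and its power are untouched. The conclusion assumes that the closing sentence in sub-item 5 is applied literally; if the general monitoring statements govern in practice, the defect is one of wording. A reader might infer that the trial is set up to report no difference in hypersensitivity. No section plans such a statement, since the SAP comparison names anaphylaxis. The change is worth making because it is cheap and safety is a stated aim.

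**What to change.** 1. In Protocol item 12, sub-item 5, split the single list in two: events that trigger immediate DSMB review, left exactly as they are, and events recorded for every subject.
2. Add to the recorded list any hypersensitivity reaction after study drug, with anaphylaxis as a separate category, and nausea and vomiting, all within the existing adverse-event assessment window.
3. Reword the restriction in sub-item 5 so that it agrees with the monitoring and attribution in sub-item 3 and the investigator's review in sub-item 7.
4. In the SAP's section on safety events for the manuscript, add these items and the tracked arrhythmias as descriptive counts by arm.
5. State that constipation is not assessed because follow-up is too short.

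The cost is two or three case-report-form lines filled from the ICU nursing chart, plus wording changes in both documents. No extra visits, staff or patients are needed. The downside is a few more non-serious events to record and grade, giving counts that describe the arms but have little power for a formal comparison.
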